In Phase I, this project will provide urgently needed data on the ways that street-level factors interact with alcohol use in a homeless population. In Phase II, this information will be used to create treatment messages that support motivation and self-efficacy.^{96,97} Motivational (derived from MI and the transtheoretical model) and self-efficacy (derived from SCT) themed messages are commonly used in technology-based alcohol interventions,⁹⁸ but mobile interventions have the additional strength of fostering self-regulation during high-craving situations through triggering goal salience and re-evaluation of short vs. long-term goals.⁹⁹ For example, SMS interventions for AUD have focused on encouraging self-regulation and planning *prior* to drinking episodes.^{100,101} For those who continue to attend shelter-based treatment, the messages will reinforce common treatment concepts. For those who discontinue shelter-based treatment, the messages may serve as a primary intervention (or at least a reminder of past concepts) in order to short-circuit alcohol use before it occurs.

C. Experimental Design and Methods

1) Methods and Procedures

Setting

Phases I and III will be conducted at the Bridge Homeless Recovery Center (i.e., the Bridge) located in Dallas, TX. The Bridge's 80 employees and on-site partners provide services (e.g., meals, mental health and substance abuse counseling, care management, housing placement, job readiness training) to approximately 85% of all homeless adults in Dallas County each year. The Bridge conducts approximately 366 new intakes each month and approximately 32% of all new intakes report current "problems with alcohol." We expect Phase I enrollment to take approximately 9 months (n=80) and Phase III enrollment to take approximately 6 months (n=40).

Screening Procedures

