Homeless adults receiving treatment at Metrocare at the Bridge will be given a flyer that briefly outlines this study. Interested individuals will be scheduled for a screening visit to determine study eligibility. We may give participants a card to remind them of their appointment time. Prior to screening, potential participants will receive information about this voluntary study and will be informed that Bridge and Metrocare services are not contingent upon study enrollment. Interested participants will sign a consent form prior to completing the screener. The screener includes questions about demographics, alcohol use, use of technology, and other questions.

We will notify subjects in real-time whether or not they are eligible to be in the study and can proceed with the baseline survey. Eligible participants will complete a separate consent form and then complete the in-person baseline assessments as described below. On the baseline they will provide identifiers that will be linked to the screener information. We will retain screening data for both eligible and ineligible participants.

Participants

Participants will be eligible if they: 1) receive a score of 8 or above on the AUDIT (a measure of alcohol dependence); 2) report consuming at least 1 drink of alcohol in the past week; 3) are receiving treatment at Metrocare; 4) are willing and able to complete the baseline and follow-up visits; 5) score ≥ 4 on the REALM-SF indicating > 6 th grade English literacy level (i.e., a 7th grade reading level is necessary to complete assessments; 12% to 14% of those screened for Projects Advance and Aspire had REALM scores < 7 th grade reading level; <1% of Bridge guests are non-English speakers), and 6) score ≥ 24 on the Mini-Mental State Exam indicating no substantial cognitive impairment. Individuals will be excluded from participating if they indicate on the screener that they would be uncomfortable wearing an alcohol sensing bracelet for 4 weeks (Phase I only). Individuals will be excluded from participating in Phase III if they participated in Phase I.

Individuals who meet the study inclusion criteria and provide informed consent will complete the baseline assessment and 4-week follow-up assessments in a space that is set aside at the Bridge specifically for this study. All participants will receive a smartphone and SCRAM at the first equipment visit, returning the devices at the end of the 4-week period.

In-person Assessments

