In-person assessments will be administered at the baseline and 4-week visits. The surveys will ask about demographics, social network, experiences with homelessness, stress/victimization, social support, mood, health, quality of life and substance use. Some of the questions are asked to evaluate the effect of the intervention (e.g., alcohol, consequences, satisfaction); other questions are asked to determine whether there are factors that moderate (e.g., self-rated mental/physical health diagnosis, stress, status, religious participation) or mediate (e.g., sleep, stress, coping) the effects of the intervention. The locator form and homelessness timeline follow-back will be administered at baseline only. Data will be collected on laptop/tablet computers using Questionnaire Development System (QDS) software. QDS utilizes a computer-administered self-interview format where each item appears on the computer screen while the program simultaneously reads the item (participants use a mouse or touch screen to

Table 1. In person assessment measures.

Background/History
Locator Form
Demographic Information Questionnaire*
Subjective Social Status ¹⁰²
Brief Homelessness Questionnaire
Homelessness Timeline Follow-Back ^{103*}
Health/Mental Health
SF-12 ¹¹⁰
Health Related Quality of Life ¹¹¹
Self-Rated Health
Tobacco Questionnaire
Inadequate Sleep
Time Line Follow-Back ¹¹² (past month alcohol)
Short Inventory of Consequences ¹¹³
Stress/Affect
Personal Victimization ¹⁰⁴
Perceived Stress Scale – Short Version ¹⁰⁵
Urban Life Stress Scale
Depression ¹⁰⁸
Interpersonal/Intrapersonal
Interpersonal Support Evaluation List
Brief COPE
Religious Participation
Treatment Satisfaction
EMI Satisfaction Survey **

*Baseline only

**Follow-up only

select answers only after QDS reads each item). Participants wear headphones so that others do not hear the survey items. Staff will be available to help participants who may have difficulty. We estimate that the baseline visit will take approximately 1 to 2 hours to complete, and the follow-up visit will take approximately 50 to 80 minutes to complete.

Equipment Visits

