A brief questionnaire will assess the initial feasibility and acceptability of the app. Specifically, in a final follow-up visit after participating in the EMA, participants will report on the helpfulness of the app and if the number of prompts on the app were appropriate. We will use statistical tests to determine if participants found the app to be helpful and if they would recommend it to others.

Effectiveness of App (Phase III only)

We will compare Phase III participants (i.e., those who received Metrocare, EMAs, and the app features including tailored treatment messages) to Phase I participants (i.e., those who received Metrocare and EMAs only) to examine the preliminary effectiveness of the app. Specifically, we will compare Phase I and Phase III participants' percent drinking days (PDD) and percent heavy drinking days (PHDD; ≥ 5 drinks for men; ≥ 4 drinks for women) using appropriate generalized linear models. We will consider the study phase as the parameter of interest estimating the treatment effect, adjusting for relevant covariates (e.g., gender, race, baseline AUD severity).

Phase I and Phase III

EMA data will be measured repeatedly and are thus correlated within subjects. Thus, our analytic approach will include generalized linear mixed model regression analysis (GLMM), a flexible analytic approach with wide use in health sciences research.¹³⁴ GLMM can handle fixed and random effect model parameters, nested designs, and repeated measures with various correlation structures.^{135,136} GLMM can also handle normal and non-normal outcomes such as dichotomous alcohol use variables, different variance functions, as well as unbalanced designs where the number of observations varies across individuals. Examples of planned GLMM analyses include: 1) testing if random assessments of alcohol urges or measures of affect (each aggregated to one rating per day) predict daily drinking status after controlling for relevant covariates (e.g., gender, race/ethnicity, depression), 2) testing if protective factors (e.g., social support, positive interpersonal interactions, prosocial location) predict alcohol use, and 3) examine trends of number of drinks and drinking days over time, accounting for dependencies of within-person repeated measures.

In addition, EMA data will allow us to examine other important questions like: 1) agreement

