between SCRAM, TLFB and EMA reports of alcohol use in this sample, and 2) the effect of episodic events (e.g., exposure to violence or other stressors) on self-efficacy and mood and what impact that has on alcohol use.

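### Require the baseline value of each drinking outcome as a covariate in the non-randomised Phase III versus Phase I comparison, chiefly to control possible confounding

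*Combined protocol and SAP*

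**What the plan says.** Section D, Effectiveness of App, compares Phase III with Phase I on PDD and PHDD by generalized linear models. Study phase is the parameter read as the treatment effect, "adjusting for relevant covariates (e.g., gender, race, baseline AUD severity"). It does not say whether PDD and PHDD are computed from TLFB or EMA.

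The cohorts are separate in people and in enrolment:
- Section C, Participants: "Individuals will be excluded from participating in Phase III if they participated in Phase I".
- Section C, Setting: "We expect Phase I enrollment to take approximately 9 months (n=80) and Phase III enrollment to take approximately 6 months (n=40").
- One eligibility rule differs by phase. People are excluded if they would be "uncomfortable wearing an alcohol sensing bracelet for 4 weeks (Phase I only").

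A baseline drinking measure is planned. Section C, In-person Assessments, states: "In-person assessments will be administered at the baseline and 4-week visits". Table 1 lists a Time Line Follow-Back ("past month alcohol") with no baseline-only or follow-up-only mark. The text adds: "The locator form and homelessness timeline follow-back will be administered at baseline only". The table footnote also marks the demographic questionnaire as baseline only. Neither restriction touches the alcohol TLFB. Section C, Equipment Visits, places phone issue about 2–3 days after baseline.

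**The concern.** No one is in both phases, so the comparison is wholly between people. The documents describe no randomisation, matching or weighting. Whatever baseline drinking difference the listed covariates do not capture, and which carries over to follow-up, is read as an app effect.

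Baseline AUD severity captures part of this, but severity is not the baseline value of the outcome. A model with only gender, race and severity would comply with the SAP. Because the list is open, the decision to add baseline drinking could also be taken after outcomes are seen. With only 40 app participants, any loss of precision matters too.

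**Working it through.** The plan gives no power, effect size, SD, significance level or correlation for this comparison, so there is no figure to reproduce. What follows shows how much the omission could matter.

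**Inputs from the documents.** 80 Phase I and 40 Phase III participants; named covariates gender, race and AUD severity; past-month alcohol TLFB at baseline and 4 weeks.

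**Assumptions.** Everyone is analysed; the test is two-sided at 5%; a standardised linear model approximates the planned models. Correlations: baseline-outcome (r_yb) 0.4–0.7, with 0.3 as a low case; severity-outcome (r_ys) 0.2–0.4; severity-baseline (r_sb) 0.2–0.5; all in steps of 0.1. Cells with a negative partial slope for severity are dropped, which keeps 41 of 48 in the main range and all 12 at r_yb = 0.3.

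**Formulas.**
- R² with severity and baseline = (r_yb² + r_ys² − 2·r_yb·r_ys·r_sb)/(1 − r_sb²)
- Baseline slope given severity = (r_yb − r_ys·r_sb)/(1 − r_sb²)
- SE with severity only = √(1/80 + 1/40)·√(1 − r_ys²) = 0.194·√(1 − r_ys²)
- Bias = slope × systematic gap in baseline drinking at equal severity
- False-positive rate = Φ(bias/SE − 1.96) + Φ(−bias/SE − 1.96)

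**Confounding: one worked cell** (r_yb, r_ys, r_sb = 0.4, 0.4, 0.5). Slope = (0.4 − 0.20)/0.75 = 0.267. A 0.3 SD gap gives bias 0.080 SD. SE = 0.194·√0.84 = 0.177. The ratio is 0.45 and the false-positive rate 7.4%.

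| Systematic gap | Bias, r_yb 0.4–0.7 | False positives | r_yb = 0.3: bias | False positives |
|---|---|---|---|---|
| 0 | 0 | 5% | 0 | 5% |
| 0.1 SD | 0.03–0.07 SD | 5.3–6.6% | not tabulated | not tabulated |
| 0.2 SD | 0.05–0.14 SD | 6.0–11.7% | 0.03–0.05 SD | 5.3–5.9% |
| 0.3 SD | 0.08–0.21 SD | 7.4–20.3% | 0.04–0.08 SD | 5.6–7.1% |

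Simulation under the same assumptions (4,000 trials per cell, four cells) checks the arithmetic only. With no systematic gap, rejection without the covariate was 4.5–5.3%. With a 0.3 SD gap it was 7.5–19.8% without the covariate and 4.8–5.5% with it.

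**Effect of recall error on the fix.** Suppose the measured baseline has reliability λ, the observed correlation is 0.5, the gap is 0.3 SD and severity is left out. The bias remaining after adjustment is 0.5 × 0.3 × (1/λ − 1): 0.04 SD at λ = 0.8 and 0.10 SD at λ = 0.6. A simulation on these assumptions gave 6–10% rejection after adjustment.

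**Precision.** The further cut in residual variance beyond severity is 1 − (1 − R²)/(1 − r_ys²).
- Weakest cell (0.4, 0.4, 0.5): R² = 0.16/0.75 = 0.213, cut 1 − 0.787/0.84 = 6.3%; the 95% half-width goes from 0.348 to 0.337 SD.
- Strongest cell (0.7, 0.4, 0.2): R² = 0.538/0.96 = 0.560, cut 1 − 0.440/0.84 = 47.7%; the half-width goes from 0.348 to 0.252 SD.
- At r_yb = 0.3 the cut is 1.6–7.3%. In the cell (0.3, 0.4, 0.5) the half-width goes only from 0.348 to 0.345 SD.
- In a quasi-binomial GLM simulation the SE fell by about 1%, 5% and 14% at assumed latent correlations of 0.3, 0.5 and 0.7: the same direction, with smaller gains.

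**The case against.** The strongest reply is that this is incomplete specification rather than error. The covariate list is introduced by example, so baseline drinking is already allowed, and one alcohol covariate is named. The two phases share the site, the AUDIT threshold, the past-week drinking criterion and the treatment provider. The plan itself calls effectiveness preliminary. All of this stands and limits the point to a clarification. It does not remove the point: being allowed is not being pre-specified, and severity covers only part of the baseline value.

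A second reply is that the gain may be small. The SAP says it will examine agreement "between SCRAM, TLFB and EMA reports of alcohol use in this sample", and the daily diary records type and quantity of alcohol, so the outcomes may well be EMA-based. If their correlation with a baseline recall measure is only 0.3, the variance cut is 2–7%. This also stands, and it is why the outcome source must be stated.

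Three stronger readings are tempting and not supported:
- A reader might infer that the phase comparison is biased. Separate enrolment windows and the Phase I-only bracelet exclusion make a systematic gap possible, but the documents give neither its size nor its direction. Chance imbalance alone does not raise the average false-positive rate above 5%.
- A reader might infer that precision is the main or a guaranteed benefit. That is the usual argument in a randomised trial. Here confounding comes first, and the precision gain depends on an unknown correlation and on the model used.
- A reader might infer that adjustment would make the phase coefficient a randomised-quality app effect. It would not remove calendar-time or SCRAM-wear differences.

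**Conclusion.** The point holds as a free improvement to the SAP. The phase coefficient rests on covariate adjustment alone, and the baseline value of each outcome is the obvious covariate not named. The first reason to require it is control of possible confounding. The ranges of 0.08–0.21 SD and about 7–20% false positives apply only if a systematic 0.3 SD gap at equal severity exists and the baseline-outcome correlation is 0.4–0.7. With no such gap the rate stays at 5%. Recall error means that adjustment reduces such bias but may not remove it. Precision is a likely second gain: 6–48% of residual variance at correlations of 0.4–0.7 and 2–7% at 0.3 in the linear approximation, and less in a quasi-binomial GLM. Every correlation and gap here is an assumption.

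**What to change.** Before Phase III outcomes are analysed, amend the SAP as follows:
- Make baseline TLFB PDD a required covariate in the PDD model and baseline TLFB PHDD in the PHDD model, alongside gender, race and AUD severity, and fix that set. The documents do not say whether the TLFB records daily quantity; if it does not, use baseline PDD in both models.
- State whether outcome PDD and PHDD come from TLFB or EMA.
- Report baseline PDD and PHDD by phase beside the estimate.
- List calendar time and any difference in SCRAM wear as limitations that adjustment does not remove.
- Reconcile who wears the SCRAM. Section C, Participants, says that all participants receive one; Section C, Equipment Visits, restricts the bracelet to Phase I.

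The cost is SAP wording and one degree of freedom per model. PDD needs no new visit or instrument; PHDD needs only confirmation that the baseline TLFB holds daily quantities.

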Study Protocol with Statistical Analysis Plan (SAP)

Development and Testing of a Just-in-Time Adaptive Smart Phone Intervention to Reduce
Drinking Among Homeless Adults

NCT03746808

Date of Continuing Review Approval: 11/02/22

Date of Document: 11/02/22

A. Specific Aims

This project will:

1. Use phone-based ecological momentary assessment (EMA) to identify environmental (i.e., geolocation), cognitive, and behavioral antecedents of alcohol use among 80 homeless adults with an AUD who are receiving shelter-based treatment.
2. Develop a “just-in-time” adaptive intervention to reduce alcohol use, including an alcohol use risk algorithm and corresponding theory-based treatment messages.
3. Examine feasibility, acceptability, and preliminary effectiveness of a just-in-time adaptive smartphone app among 40 homeless adults with an AUD who are receiving shelter-based treatment.

B. Background and Significance

An estimated 6.2% of US adults will be homeless at some point in their lifetime.¹ Homeless adults have higher rates of disease, greater risk of interpersonal violence, shorter life expectancies, and disproportionately higher health care utilization and costs compared to housed individuals.²⁻⁵ A significant contributor to morbidity and mortality among homeless adults is the high prevalence of alcohol use.⁶⁻⁹ Approximately 33% of homeless adults have current alcohol dependence,^{10,11} a rate nearly 8 times that of the general population.¹² Although shelter-based treatments are common,¹³ compliance is typically poor.⁹ Identifying factors that influence alcohol use would significantly improve our ability to develop effective interventions and engage homeless adults in treatment.

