Social Support and Interactions
Treatment Attendance
Current Stressors & Perceived Stress
Alcohol Consumption
Other Substance Use
Core/Random/Event Sampling
Affect/Stress
Urge to Drink
Alcohol/Money Availability
Social setting/Location
Recent Alcohol Consumption
Expectancies
Abstinence Motivation
Abstinence Self-Efficacy
New/Ongoing Stressful Events*
Reasons for Drinking*
Modified Conflict Tactics Scale

*Drinking assessments only

sampling, and event sampling. Random sampling and daily diary EMAs will be initiated by the phone. The phone will audibly and visually cue these EMAs for 30 seconds. If the participant has not responded after 5 prompts, the assessment will be recorded as missed. Event sampling is initiated by participants if/when they consume the first drink in a day. On average, random and event sampling assessments take 2 minutes to complete and daily diary assessments take less than 5 minutes to complete.

Daily Diary EMAs will be completed each day (prompted 30 minutes after waking time); questions will ask about the previous day and current experiences. Alcohol consumption will be assessed with the item “Did you drink any alcohol yesterday?” If the participant answers “yes,” he/she will be prompted to indicate the type and quantity of the alcohol that was consumed. Additional items will assess sleeping arrangements from the prior night, social support and types of social interactions, discrete stressors, other substance use, and treatment session attendance. Daily Diary assessments will cease after 4 weeks.

Random Sampling will occur 4 times each day, during each participant’s normal waking hours. Participants will rate their affect by indicating the extent to which they agree or disagree with each of thirteen statements: I feel irritable, happy, content, angry, sad, worried, miserable, restless, stressed, hostile, calm, bored, and depressed. In addition, participants will describe their current environment (e.g., shelter, work, outside, bar) and social setting (e.g., alone, with others, with others who are drinking). Alcohol urges, alcohol/money availability, drinking start/stop time, recent drinking, expectancies, motivation for abstinence, and abstinence self-efficacy will also be assessed during random sampling. Random assessments will cease after 4 weeks.

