Event Sampling will be available to participants on demand. Participants will be instructed to click the “Record Drink” button if/when they have their first drink of a day. Drinking assessments will include all items from the random assessments and will query about the reinforcing value of the drink(s) and causes of the drinking episode.

Geolocation. Consistent with previous work,^{19,20,51} smartphones will collect geo-location coordinates about every 5 minutes. The aim of this study is to identify psychological, social, and contextual variables that predict drinking and heavy drinking days. Previous studies have found that continuous “breadcrumb” tracking can be used to identify important health risk factors.^{19,20,58} We will remove all personal information from the phone once it is returned to us.

Alcohol Sensor

Biosensors can provide a continuous estimate of blood alcohol concentration (BAC) based on the concentration of alcohol in perspiration on the skin.⁵²⁻⁵⁹ The device with the most extensive evaluation is the SCRAM bracelet (Alcohol Monitoring Systems, Littleton, CO), which is worn on the ankle. In Phase I, all participants will wear the SCRAM for 4 weeks. SCRAM has an electrochemical sensor that samples the vapor near the skin every 30 minutes for ethanol, and stores readings for later retrieval. Data from the SCRAM is downloaded to a computer via USB cable, using a 16-digit key and password-protected software. The SCRAM is water resistant and cannot be removed without cutting the strap. The SCRAM system provides alerts if the bracelet sensors detect an obstruction or other tampering. At the 2-week equipment check-in, our staff will review participant readings and any alerts and will address any malfunction or evidence of tampering. To mitigate any potential risk to subjects while wearing the SCRAM monitor:

- a. Law enforcement officers cannot obtain the information even if subjects are taken to jail. SCRAM data are encrypted and need to be connected to the research computer in order to download the data.
- b. The Certificate of Confidentiality (COC) protects investigators from having to disclose SCRAM data to law enforcement or anyone else.
- c. Subjects can cover up the ankle monitor with their clothes and always decline participating in the study.
- d. Subjects will be informed through the consent form that the SCRAM ankle bracelet may draw unwanted attention by law enforcement (and possibly others) to them.

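### The one Phase I predictor model with a stated time unit has no time order, so run on same-day data it cannot tell an antecedent of drinking from a consequence

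*Combined protocol and SAP*

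**What the plan says.** Section A, Aim 1, is to "identify environmental (i.e., geolocation), cognitive, and behavioral antecedents of alcohol use" in 80 Phase I participants.

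Section D, under Phase I and Phase III, opens its list with "Examples of planned GLMM analyses include". The first item is "testing if random assessments of alcohol urges or measures of affect (each aggregated to one rating per day) predict daily drinking status", adjusted for covariates. The second relates protective factors to alcohol use and gives no time unit. The third is a trend over time with no antecedent as predictor. A closing question on episodic events also gives no time unit.

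On data collection, Section C states:
- Random prompts: "Random Sampling will occur 4 times each day", across waking hours. Items include "Alcohol urges, alcohol/money availability, drinking start/stop time, recent drinking".
- Daily diary: it asks about drinking on the previous day. A participant who drank is "prompted to indicate the type and quantity of the alcohol that was consumed". Time is not mentioned.
- Record Drink button: pressed "if/when they have their first drink of a day".
- SCRAM (Phase I): it "samples the vapor near the skin every 30 minutes for ethanol".

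The Geolocation paragraph sets a day-level purpose, predicting drinking days and heavy drinking days. The Message Content paragraph works with windows of about 4 and 4-8 hours. The Risk Algorithm paragraph draws on variables found in Phase I and mentions an 8-hour build-up of negative affect or stress.

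**The concern.** An antecedent has to come before the drink. Four prompts spread over the waking day will often straddle the first drink, and nothing in the plan removes those that come after it. Averaging them into one value per day and relating that value to whether the person drank that day mixes ratings from before and after the event.

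If mood or urge changes once drinking has started, the daily coefficient partly measures that change. It can create a precursor that does not exist, cancel one that does, or reverse its sign. If next-day drinking was intended, the order is right but the horizon becomes about a day. In either case, one rating per day cannot show a pattern that builds over 8 hours.

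What is at stake is the answer to Aim 1.

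**Working it through.** The plan gives no power, effect size or error rate for Aim 1, so there is no figure of its own to reproduce. What follows is an illustration.

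**Inputs from the documents.** 80 participants, 28 days, 4 prompts a day; 82% completion (an earlier sample, Phone Assessments). This gives 80 × 28 = 2,240 person-days, 8,960 prompts and about 7,347 completed ratings.

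**Assumed inputs.** Daily value = mean of completed ratings; 16 waking hours; drinking on 50% of days; first drink uniform 4-12 h after waking; within-person SD of a rating = 1; correlation ρ between same-day ratings of 0, 0.3 or 0.5; a precursor effect *a* in the 4 h before the first drink; a shift *b* after it.

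**Step 1: share of ratings after the first drink.** The mean first-drink time is 8 h, so (16 − 8)/16 = 50% of drinking-day ratings come later. With first drinks at 2-8 h the share is (16 − 5)/16 = 69%; at 8-14 h it is (16 − 11)/16 = 31%. The 4 h before the drink hold 4/16 = 25%.

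**Step 2: shift in the daily mean on drinking days.** d = 0.25*a* + 0.50*b*.

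**Step 3: its standard error.** With *c* completed ratings, binomial (4, 0.82) given at least one, E(1/c) = 0.330. The variance of a daily mean is ρ + (1 − ρ) × 0.330, which is 0.330, 0.531 or 0.665. With 1,120 drinking and 1,120 other days and person-centring, SE = √[variance × (2/1,120) × (28/27)] = 0.0247, 0.0314 or 0.0351.

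**Step 4: chance of a significant result.** Φ(|d|/SE − 1.99), where 1.99 is the two-sided 5% point of t with 79 df. Simulation of the daily model (person-centred linear probability model, person-clustered SE) is in brackets.

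| Setting | d | ρ = 0 | ρ = 0.3 | ρ = 0.5 |
|---|---|---|---|---|
| a = 0, b = +0.1: false predictor | 0.050 | 51% (50%) | 35% (33-34%) | 29% (28%) |
| a = 0, b = +0.2: false predictor | 0.100 | 98% (98%) | 88% (86-87%) | 80% (80-81%) |
| a = +0.3, b = −0.3: wrong sign | −0.075 | 85% (83-86%) | 66% (68-69%) | 56% (55-62%) |
| a = +0.3, b = 0: true precursor found | 0.075 | 85% (83%) | 66% | 56% |

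With a = +0.3 and b = −0.15, d = 0.075 − 0.075 = 0: the precursor is cancelled and found in about 2% of runs.

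**Step 5: time-ordered model.** Each pre-drink rating is related to a first drink within 4 h, with time of day in the model. At ρ = 0 a run has about 5,514 such ratings, 916 of them followed by a first drink within 4 h. With a = 0 and b = +0.2 it rejects in 4.5% of runs; with a = +0.3 it detects the precursor in 100%, whether b is 0, −0.15 or −0.3. At ρ = 0.3 and 0.5 it stays near 5% false and 100% detection.

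**Step 6: a second set of assumptions.** Logistic GEE, 40% drinking days, first drink uniform over 16 h, no true antecedent, shift in units of the within-day SD. The daily mean of all ratings rejects in 5.5% of runs at shift 0, 17.5% at 0.1 and 86.5% at 0.25. A daily mean of pre-drink ratings only rejects in 4.5-6% for every shift from 0 to 1.0.

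**The case against.** The strongest reply is that this criticises an illustration for lacking detail. The list is headed as examples, and the word predict can imply order. The algorithm text expects slopes and volatility from the GLMMs, which one value per day cannot give within a day, so the intended set of models is probably wider than this one. That stands in part: the plan does not say that same-day data will be used regardless of order. But no other listed analysis supplies the order, so the gap remains.

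Second, a day-level model fits the day-level purpose in the Geolocation paragraph. That stands, and is a reason to keep a daily model. Its predictors must still precede the drink if they are to be called antecedents.

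Third, the sizes rest on assumptions. That stands. With no post-drink shift there is no bias, and higher correlation between same-day ratings lowers the error rates, as the table shows. The time-ordered model is also favoured by testing a 4-hour precursor with a 4-hour window; with an 8-hour precursor, no shift and uncorrelated ratings, both models detect it in 100% of runs.

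Fourth, the remedy has its own errors. In runs with uncorrelated ratings, no precursor and a +0.2 SD shift, first-drink timing error of SD 1 h gives about 7% false rejections and SD 2 h about 19%, against 97% for the daily model. In the worst case tried (2-hour precursor, −0.3 SD shift, SD 2 h error, 30% of drinking days without a time), it detects the precursor in only 10%; the daily model then has the wrong sign in 99%.

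A reader might also infer that the intervention's messages will be mistargeted. The documents do not support that: they weight algorithm variables iteratively by their relation to lapse and do not say that the weights come from the daily model.

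**Conclusion.** The point holds as a conditional one about Aim 1, and the change should be made. The only predictor model with a stated outcome time unit leaves time order open. On same-day data it cannot separate what precedes drinking from what follows it.

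Under the assumed inputs with ρ from 0 to 0.5, the daily model finds a false predictor in about 28-50% of runs at +0.1 SD after drinking and 80-98% at +0.2 SD. With a +0.3 SD precursor and a −0.3 SD shift, it has the wrong sign in about 55-86%. These figures depend on the post-drink shift, drinking frequency and first-drink times, none of which the documents give.

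Two stronger conclusions do not follow. The daily model is not invalid in itself: without a post-drink shift its error rate is correct and it loses only power. And the comparison of percent drinking days and percent heavy drinking days between phases does not use these ratings, so it is unaffected.

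**What to change.** Add one paragraph to Section D for Aim 1:

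- **Unit:** each random EMA completed before that day's first drink.
- **Outcome:** first drink within the next 4 h, with 8 h as a sensitivity analysis.
- **Model:** GLMM with within-person centred ratings, a random intercept and time of day.
- **Timing:** reported start times and Record Drink entries, checked against SCRAM. As a sensitivity analysis, leave out days on which the EMA and SCRAM times differ by more than a pre-set limit.
- **Daily model:** keep it for the day-level purpose, but build the daily value only from ratings before the first drink, or label the all-ratings version an association. Pre-drink ratings come from earlier in the day than ratings on dry days, so account for time of day here too.

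The cost is a paragraph and some extra analysis. No new data are needed: the times, first-drink reports and SCRAM readings are already collected in Phase I, and Section D already plans to examine agreement between SCRAM and EMA. The drawbacks are first-drink timing error, loss of drinking days with no recorded time, and loss of days when drinking starts at or soon after waking and leaves no earlier rating. In the illustration no one drinks before 2 h after waking even in the widest range, so it does not cover that last loss. Count and report the days lost.
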